3. STUDY OBJECTIVES AND DESIGN

3.1 Hypothesis and primary objective

Overall aim: To compare the diagnostic, therapeutic and clinical outcomes of three diagnostic strategies based on CXR (standard care), low-dose CT scan (LDCT) or lung ultrasonography (LUS) in elderly patients with suspected community or nursing-home acquired pneumonia in the ED.

Primary objective: To evaluate whether a diagnostic strategy using LDCT compared with CXR leads to a more accurate diagnosis in suspected pneumonia.

Secondary objectives:

Diagnostic objectives:

- To assess the difference in diagnostic accuracy for patients with suspected pneumonia using LUS compared to CXR, and using LUS compared to LDCT
- To assess sensitivity and specificity of CXR, LDCT and LUS; the number of additional imaging studies and invasive procedures prescribed during the acute setting; the imaging studies needing unmasking in emergency; the incidentalomas.

Treatment objectives: to assess whether there is a difference between the diagnostic strategies in:

- Antibiotic consumption up to one month

Clinical objectives: to assess whether there is a difference between the diagnostic strategies in:

- Time to clinical stability
- Length of hospital stay

- Unplanned transfer to the intensive care unit or operating room
- Admission to rehabilitation/long-term care facility (LTCF) up to 3 months
- All-cause mortality up to 3 months
- All-cause readmission up to 3 months
- Quality of life at admission, discharge and 3 months

Cost outcomes

Diagnosis concordance between physicians at the ER and experts

The association of biomarkers and the presence of an infiltrate.

GEROBIOTA objectives

To identify factors associated with the probability of pneumonia, and aspiration pneumonia, 1 month and 1 year mortality, 1 year readmission and to create a biobank allowing the assessment of inflammation, immune status and genetic markers.

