8) Clinical outcomes: We will use Kaplan Meier's estimates to evaluate the time to clinical stability over 15 days in each arm, and a log-rank to compare them. Patients who die in the first 2 weeks will be censored at day 15 (i.e. considered has never reaching clinical stability). The Mann-Whitney test will be used to compare the length of hospital stay between the groups. The proportion of patients with an unplanned transfer to the ICU or operating room will be reported by arm and compared between the arms using a logistic regression model adjusted for sites. All-cause mortality during the 3-month follow-up will be investigated with Kaplan Meier's survival curves, and compared between the arms using a log-rank test stratified on sites. Readmissions during the 3-month follow-up will be investigated using survival models with competing risk. Death before readmission will be the competing event.

9) Cost outcomes: Mean cost per patient will be assessed and compared between arms using multiple linear regression models adjusted for sites. Reweighted estimators will be used to account for censoring.

10) Interagreement rate for the probability of pneumonia rated on a 3-level Likert scale: the agreement between raters participating to the trial and a consensus of two experts will be investigated by using kappa statistics.

11) The association between biological markers (CRP and PCT) and infiltrates will be assessed by differences in the mean levels of markers between patients with and without infiltrates and tested by using t test. Transformations on markers will be applied if needed. Multiple linear regression models will be used for adjustment. Similar methods will be used to investigate the association between markers and the probability of pneumonia rated on the 3-level scale. The analyses will be conducted for each arm.

Interim and safety analyses

There will be no comparative analysis for efficacy or futility. An initial safety analysis will be performed after 200 patients have reached the 1-month follow-up. The study's data manager will ensure that the data will be exported with "scrambled" allocation labels and that study investigators do not have access to the data. The results will be transmitted to the principal investigators and the safety monitoring board. The latter will be free to lift the blind if deemed necessary, and will be asked to make the final decision on the continuation of the study without modification, or terminating the study.

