#### Clinical outcomes

- Time to clinical stability
- Hospital admission
- Length of hospital-stay
- ICU admission
- Transfer to rehabilitation or long-term care facility (LTCF)
- All-cause ICU readmission
- In-hospital mortality
- All-cause mortality at 30 days and at 90 days
- Quality of life at 30 days and at 90 days

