- **All-cause mortality within 30 days** will be defined as a death date (*death\_date* or *deathdate*) occurring within **30 days** of the emergency entry date (*emergencydate*)

- **All-cause mortality within 90 days** will be defined as a death date (*death\_date* or *deathdate*) occurring within **90 days** of the emergency entry date (*emergencydate*)

- **In-hospital mortality** will be defined as a death occurring on or before the hospital discharge date (*hospital\_discharge\_date*), based on the recorded death date (*death\_date* or *deathdate*)

- **All-cause readmission within 90 days** after initial emergency admission/evaluation will be defined as a readmission date (*readmission\_date*) occurring within **90 days** of the emergency entry date (*emergencydate*)

- **Quality-of-life at 30 days and 90 days** (*eq5d\_score*)

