**Quality-of-life at admission\***

---

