#### 8.2.3.4 Clinical outcomes

- **All-cause mortality at 30 days** will be
  - estimated by arm using the Kaplan-Meier method
  - compared between arms through pairwise comparisons using a log-rank test stratified by centre (three pairwise tests will be performed)
  - and the complementary log-log transformation will be applied to calculate the 95% confidence intervals for the 30-day survival estimates
- **All-cause mortality at 30 days** will be described only
- **In-hospital mortality**
  - will be described by arm as count and percentages
  - will be compared between arms using a logistic regression model adjusted on centre. Odds ratio will be reported with 95% confidence intervals
- Number of patients hospitalised after emergency and number of patients discharged after emergency will be described by arm as count and percentages
- **Length of hospital stay**
  - Will be analysed **among all randomized patients, and repeated among hospitalized patients only** (excluding those discharged after emergency department presentation)
  - Will be compared between arms using a linear regression model adjusted on centre with a bootstrap method for 95%CI.
  - Pvalues will be computed by inverting the corresponding confidence interval (Thulin 2024: modern statistics with R).
- **Unplanned transfer to the ICU/IMCU within 30 days after initial admission/evaluation**
  - Will be analysed **among all randomized patients, and repeated among hospitalized patients only** (excluding those discharged after emergency department presentation)
  - Will be described by arm as count and percentages
  - Will be compared between arms using a logistic regression model adjusted on centre. Odds ratio will be reported with 95% confidence intervals.
- The following outcomes will be described by arm as count and percentages **in patients discharge alive**. Those outcomes will not be compared between arms:
  - **Admission to rehabilitation through 3 months in patients discharge alive**
  - **Transfer to LTCF through 3 months in patients discharge alive**
  - **All-cause readmission to acute care setting in patients discharge alive**
  -
- The **quality of life 30 days and 90 days** will be described by arm as median and IQR **in patients discharge alive**. Quality of life will not be compared between arms

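### Readmission: the SAP replaces the protocol's competing-risk analysis with uncompared percentages among patients discharged alive, and does not declare the change

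*SAP*

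**What the plan says.** **Protocol.** Section 3.1 words the clinical aims as contrasts: "Clinical objectives: to assess whether there is a difference between the diagnostic strategies in" a list that includes all-cause readmission up to 3 months and "Quality of life at admission, discharge and 3 months". Section 3.2 lists readmission to acute care at both 1 and 3 months. Section 5.1, item 8, gives the method: "Readmissions during the 3-month follow-up will be investigated using survival models with competing risk", with death before readmission as the competing event. Section 4.4 says that patients lost to follow-up are censored after their last visit. Section 5.1 names no analysis for quality of life.

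**SAP.** Section 8.1.2.4 works from dates: all-cause readmission within 90 days "after initial emergency admission/evaluation will be defined as a readmission date" no more than 90 days after emergency entry. Death is also dated. Section 8.2.3.4 then reports rehabilitation, long-term care and readmission as counts and percentages in patients discharged alive, and states: "Those outcomes will not be compared between arms". Quality of life at days 30 and 90 is given as median and IQR in the same subset: "Quality of life will not be compared between arms". The summary list in section 3.3.2 calls the readmission outcome "All-cause ICU readmission". Section 9 names one abandoned protocol analysis, time to clinical stability.

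**The concern.** Readmission is one of the outcomes through which a wrong or late diagnosis in the ED could reach the patient. The protocol therefore asks for a between-strategy difference and chooses a method that allows for death. The SAP keeps the outcome but removes the contrast, the population and the handling of death.

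Three things are at stake. First, no effect estimate, interval or test is planned for a stated objective. Second, the groups shown side by side are no longer the randomised groups, because in-hospital mortality decides who is in the denominator and is itself an outcome the SAP compares between arms. Third, a reader of section 9 would conclude that only time to clinical stability had been dropped.

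**Working it through.** **1. The documents side by side**

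| Element | Protocol | SAP |
|---|---|---|
| Question | Difference between strategies, up to 3 months (3.1) | Described only (8.2.3.4) |
| Time points | 1 and 3 months (3.2) | 90 days only (8.1.2.4), although 3.4 schedules readmission at days 30 and 90 |
| Population | Intention to treat (5.1) | Patients discharged alive (8.2.3.4) |
| Death | Competing event (5.1, item 8) | In-hospital deaths removed; later deaths not treated as competing events |
| Losses | Censored after last visit (4.4) | Complete cases (8.4) |
| Label | Readmission to acute care (3.2) | ICU readmission (3.3.2); all-cause readmission (8.1.2.4); readmission to acute care (8.2.3.4) |
| Declared as changed | n/a | No (section 9) |

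**2. Clock and denominator.** The SAP counts readmission from emergency entry, but a patient joins the denominator only at live discharge. Someone discharged on day 20 has at most 90 − 20 = 70 days in which to be readmitted. The percentage therefore partly reflects length of stay, another outcome. A cumulative incidence from ED entry in all patients, with death competing, avoids this.

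**3. Size of the denominator effect.** Suppose 1% of a 165-patient arm die in hospital: 0.01 × 165 = 1.65. With an assumed 20% readmission, 33/165 = 20.0% becomes 33/(165 − 1.65) = 33/163.35 = 20.2%. The shift is 0.2 points per 1% of deaths, so this alone is a small distortion.

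**4. Is a contrast feasible?** The documents give no sample size for readmission, so the arm size comes from the primary outcome. For 68% against 84%, two-sided 0.05, 90% power, pooled mean 0.76:

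n = [1.96 × √(2 × 0.76 × 0.24) + 1.282 × √(0.68 × 0.32 + 0.84 × 0.16)]² / 0.16² = 148 (rounded up)

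This agrees with the plan's 150, and 150 × 1.1 = 165. The documents give no readmission rate, so the risks below are assumptions. The 95% CI half-width for a risk difference with equal risk p and n per arm is 1.96 × √(2p(1 − p)/n). The detectable increase is for 80% power at two-sided 0.05.

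| Assumed 90-day risk | Half-width, n = 150 | Half-width, n = 165 | Detectable increase |
|---|---|---|---|
| 10% | 6.8 points | 6.5 points | 11 to 12 points |
| 20% | 9.1 | 8.6 | about 14 |
| 30% | 10.4 | 9.9 | 15 to 16 |
| 40% | 11.1 | 10.6 | 15 to 16 |

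These figures assume complete follow-up; censoring would widen the intervals somewhat. Only large differences could be demonstrated, but an estimate with its interval is informative.

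**5. Quality of life.** The objective is also a difference, but no protocol method exists to restore. Baseline timing is unclear: the protocol measures quality of life at admission, discharge and 3 months, the SAP schedule (3.4) at ER discharge, day 30 and day 90, while SAP Table 1 lists "Quality-of-life at admission".

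**The case against.** The trial is powered for accuracy only, and the SAP states no multiplicity control, so limiting formal secondary tests is defensible. Patients who die in hospital cannot be readmitted, which makes discharged alive a natural descriptive denominator. SAP 8.2.3.4 does compare 30-day mortality, in-hospital mortality, ICU/IMCU transfer and length of stay, and 8.2.3.3 compares antibiotic-free days. By-arm counts will appear, and a reader could form a crude risk difference from them. The SAP's own secondary objective (2.2) covers only the two LUS contrasts.

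Much of this stands, and several stronger readings fail:

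- A reader might infer that the objective cannot be answered at all or that harm would go unseen. The reported counts and the other compared outcomes say otherwise.
- A reader might infer that patients lost to follow-up count as not readmitted. No passage says so: SAP 8.4 specifies complete cases and protocol 4.4 specifies censoring.
- A reader might see three different readmission outcomes. The definitions in 8.1.2.4 and 8.2.3.4 read together as the protocol's outcome; only the ICU label is out of line.
- A reader might credit the protocol with a centre-stratified test or a risk difference for readmission, or with a quality-of-life method. It names none of these.

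The objection does not explain why a prespecified comparison was removed while one that section 9 says was not prespecified, in-hospital mortality, was added. Concern about multiple testing argues for estimates with intervals, not for omitting the contrast. Nor does it excuse the silence in section 9.

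**Conclusion.** The point holds for readmission. A protocol objective with a named method has become an uncompared percentage in a subset defined after randomisation, without declaration. The wrong label in SAP 3.3.2 and the missing 30-day definition are separate textual faults.

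The main loss is the missing contrast and the handling of death. The arithmetic shift from the denominator is small, about 0.2 points per 1% of in-hospital deaths at an assumed 20% readmission. A restored analysis would give a 95% CI half-width of about 7 to 11 points if 90-day risk lies between 10% and 40%, a range that is assumed because the documents give no rate.

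For quality of life the case is weaker. The SAP departs from the objective but not from any named analysis, so a comparison is desirable rather than owed. Its absence still needs a stated reason. The primary analysis is unaffected.

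**What to change.** 1. In SAP 8.2.3.4, replace the readmission bullet with the cumulative incidence of all-cause readmission to acute care, from ED entry to day 90 and also read at day 30. Use the full analysis set, with death before readmission as competing event and losses censored at last contact. Report pairwise between-arm estimates with 95% CIs, preferably accounting for centre as for the other outcomes. The percentage among patients discharged alive can stay as a supplementary description.
2. Add the 30-day definition to 8.1.2.4 and correct the ICU label in 3.3.2.
3. List and justify in section 9 any departure that remains, including the uncompared rehabilitation, long-term care and quality-of-life outcomes, which the protocol also frames as differences.
4. Optional: report pairwise differences in EQ-5D with 95% CIs, adjusted for centre and the admission value. State explicitly how deaths are handled, and first settle which measurement is the admission value.

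The cost is a few lines of text and one standard secondary analysis on dates already collected, with limited precision. SAP section 1 says that the document was finalised before data analysis is started, so on that timeline the change can still be made as a prespecified one.

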#### 8.2.4 Assessment of statistical assumptions

The Cochran-Mantel-Haenszel method requires that stratification by centre is appropriate, with sufficient patient numbers per centre to provide reliable estimates. Since the study will include approximately 500 patients distributed across three centres, it is expected that the sample size per centre will be large enough to satisfy this requirement and provide stable stratified estimates.

Regression models (linear or logistic) assume independence of observations; homoscedasticity and normality of residuals for linear models; and linearity of the logit for logistic regression (when continuous predictors are included). Survival analyses assume non-informative censoring and proportional hazards over time. For linear models, the assumptions will be checked graphically (scatter plots, scale-location plots, residual-versus-fitted values plot). The proportionality of hazards will be graphically checked with the log-minus-log plot and regression coefficients based on categorizations of the continuous variable. The proportionality of log-odds will be checked with the regression coefficients of categorized variables. If significant violations of key assumptions are detected (e.g., non-normality of residuals, heteroscedasticity, or sparse data in logistic models), alternative methods (e.g., data categorization, exact methods, or non-parametric approaches) or sensitivity analyses will be considered and documented.

### 8.3 Interim analyses

There will be no interim analyses for efficacy or futility. An initial safety analysis was performed after 200 patients completed the 1-month follow-up, following which the Data and Safety Monitoring Board (DSMB) made the final decision to continue the study without modifications.

### 8.4 Missing data

Analyses will be conducted using a complete case approach, including only participants with fully observed data for the variables of interest, as the amount of missing data is expected to be low. The extent and reasons for missing data will be assessed and reported by study arm.

### 8.5 Safety evaluation

Safety analyses will consist of descriptive statistics by study arm for all reported adverse events (AEs), serious adverse events (SAEs), and other safety-related outcomes collected during the study period.

### 8.6 Statistical software

All statistical analyses will be conducted using R statistical software (version 4.2.2 or later).

## 9. Statistical deviation from the protocol

The following exploratory analysis, not specified in the protocol but added before the database was locked, will be conducted.

1. Studying in-hospital mortality was not prespecified in the protocol. This variable was finally retained due to its clinical relevance and availability in the collected data, providing complementary insight into short-term patient outcomes
2. Subgroup analyses according to
  - Patients with chronic pulmonary disease
  - Patients with obesity (BMI $\geq$ 30)

Indeed, CT may be a better diagnostic strategy compared to others in those patients, and this could lead to recommendations for patients with a chronic pulmonary disease and for patients with obesity.

The following analyses were part of the initial protocol and will finally not be conducted:

1. Time to clinical stability was found to be difficult to compute reliably during SAP drafting and will therefore not be analysed

### OCTOPLUS expert panel method

#### **Aim**

Adjudication of the diagnosis of pneumonia in OCTOPLUS by experts.

A patient's diagnosis will be considered as accurate if the clinician's diagnosis and the panel of experts agree (true positive and true negative diagnoses).

#### **What is the OCTOPLUS trial?**

This is a multicentre randomised superiority clinical trial with three parallel arms comparing 3 diagnostic strategies for the pneumonia in patients >65y. Patients will be allocated in the ER to a strategy based on either chest-X ray (CXR), low-dose CT scan (LDCT) or lung ultrasonography (LUS), the CXR arm being the standard of care. All imaging modalities will be performed but the results of two of them will be masked during 5 days to the patients, the physicians in charge and the investigators according to random allocation. The primary objective is to compare the accuracy of LDCT versus CXR-based strategies.

<http://dx.doi.org/10.1136/bmjopen-2021-055869>

### **Description of the adjudication process/expert panel: modified Delphi methods with 3 rounds**

A panel of experts (senior clinicians, including internists, geriatricians and radiologists), blinded to the allocation arm and the probability of pneumonia estimated by the treating clinician, will retrospectively rate the probability of pneumonia based on all available patient data present in the medical records, including the reports and images of the 3 imaging modalities: CXR, LDCT, and LUS. It will be centralized for all including centres and done as follows:

**1st round.** Each expert will individually assess for each patient the probability of pneumonia on a 5 Likert scale (very likely or confirmed, probable, possible, unlikely, excluded).

Patients with a very likely/confirmed, probable and possible probability of pneumonia will be considered as having a pneumonia. Patients with an unlikely or excluded probability will be considered as not having pneumonia; for these patients, an alternative diagnosis will be proposed by the panel.

Hôpitaux  
Universitaires  
Genève

CENTRE DE  
RECHERCHE CLINIQUE

UNIVERSITÉ  
DE GENÈVE

For all cases, the panel will be asked to give a concomitant diagnosis (another pathology concurring to the symptoms presented, e.g. acute heart failure complicating an episode of pneumonia).

The panel of experts will also be asked to adjudicate the presence of aspiration pneumonia\* and viral pneumonia.

**2nd round.** Pairs of experts will discuss discordant cases.

**3rd round.** In a plenary session and in the presence of an expert in thoracic imaging and an expert in LUS, all experts will achieve consensus on discordant cases. This final decision will serve as the reference diagnosis.

To promote agreement, the experts will be trained before the adjudication.

## Methods

### 1/ Panel constitution

The experts will be randomly assigned to a pair. Each pair will include one expert from the study staff and a second expert not involved in the study.; The pair same pair will assess the patients on round one and two.

Both experts must be physicians in current clinical practice (at least part-time); they must be regularly confronted with patients with a suspicion of pneumonia; they must be board-certified in internal medicine, infectious disease, lung disease, intensive care medicine, or emergency medicine; and they must have at least 5 years of clinical experience.

Radiological experts who will attend the 3rd round of the adjudication will be board-certified in radiology and experienced in thoracic imaging. Ultrasonography experts will also be present, they will be board-certified.

